6.6.2 Excluded Medications

Excluded medications include all steroid medications, other IPs, as well as ketoconazole, St. John's wort and Chinese medicine therapies.

Concurrent use of ACTH, prednisone or other glucocorticoid is not permitted, nor use of the strong inducers of CYP3A4 (except approved ASMs: carbamazepine, phenytoin derivatives, phenobarbital, or primidone), rifampin and St. John's Wort. Participants on ACTH, prednisone, or other systemically (non-inhaled or topical) administered steroids should be off the product > 28 days prior to screening. Rifampin and St John's Wort must be discontinued at least 28 days before Visit 2, study drug initiation. Chinese medicine therapies must be discontinued at least > 28 days prior to screening.

Note: Concomitant intranasal or PRN topical steroids for dermatologic reactions and allergic rhinitis are allowed.

Products containing THC or non-approved CBD are excluded during treatment. Tetrahydrocannabinol or non-approved CBD should be washed out for at least 4 weeks prior to screening. Participants with a positive result on THC or CBD laboratory tests, and who do not

have an explanatory Epidiolex®/Epidyolex® prescription, will be excluded or withdrawn from the study.

6.7 Intervention After the End of the Study

Participants may be eligible for continued treatment with GNX in an OLE. In the OLE, treatment can continue until the sponsor terminates the development of the IP in TSC or GNX has been approved and marketed in the participants' respective country.

7 DISCONTINUATION OF STUDY INTERVENTION AND PARTICIPANT DISCONTINUATION/WITHDRAWAL

7.1 Discontinuation of Study Intervention

In rare instances, it may be necessary for a participant to permanently discontinue study intervention. If the IP is discontinued at any time, participants should follow the 2-week taper schedule unless otherwise medically indicated. If the participant discontinues during the maintenance period, evaluations listed for the Early Termination Visit (Visit 12; [Table 1](#)) are to be performed as completely as possible along with the end of study and safety follow-up assessment, as appropriate. Comments (spontaneous or elicited) or complaints made by the participant must be recorded in the source documents. The reason for termination, date of stopping the IP, and total amount of the IP taken must be recorded in the eCRF and source documents. Discontinuation of the IP due to AEs must also be reflected on the AE eCRF page. Participants who discontinue IP should undergo a 2-week or shorter taper period, as clinically indicated. These participants will have a visit 2 weeks after the end of taper to complete the safety follow-up assessments.

See the SOA ([Section 1.3](#)) for data to be collected at the time of discontinuation of study intervention and follow-up and for any further evaluations that need to be completed.

The reason for early discontinuation of the IP must be determined by the investigator and recorded in the participant's source documents and on the eCRF. If a participant is withdrawn for more than 1 reason, each reason should be documented in the source document and the most clinically relevant reason should be entered on the eCRF.

Reasons for early termination include but are not limited to the following:

- AE (including pregnancy).
- Protocol violation/protocol deviation.
- Withdrawal by participant or parent(s)/LAR(s).
- Lost to follow-up.
- Lack of efficacy.
- Death.
- Investigator decision.

7.2 Discontinuation/Withdrawal From the Study

All participants or his/her parent(s)/LAR(s) reserve the right to withdraw from the study at any time, as stated in the informed consent/assent form. The investigator may discontinue participants from the clinical study for any of the following reasons:

- Participant is found to have entered the study in violation of the protocol.
- Participant requires the use of a disallowed concomitant medication.
- Participant's condition changes after entering the clinical investigation so that the participant no longer meets the inclusion criteria or develops any of the exclusion criteria.
- Participant or parent(s)/LAR(s) withdraws consent or assent to participate in the study.
- Participant is noncompliant with the procedures set forth in the protocol.
- Participant experiences an AE/SAE that warrants withdrawal from the study.
- Any laboratory, medical, or clinical finding for which clinical intervention should take precedence over study participation. This includes:
 - AST/SGOT or ALT/SGPT $> 3 \times$ ULN.
 - Total bilirubin levels $> 1.5 \times$ ULN.
 - eGFR < 30 mL/min.
- It is the investigator's opinion that it is not in the participant's best interest to continue in the study.

Decisions to discontinue the study will be made at each participating site by the investigator. If feasible, the reason for discontinuation should be discussed with the sponsor's medical monitor prior to participant's discontinuation. Participants who discontinue the IP during the maintenance period will continue to record daily seizure frequency at minimum until the completion of the maintenance period.

At the time of discontinuing from the study, if possible, an Early Termination Visit (Visit 12) should be conducted as shown in the SOA ([Section 1.3](#)). At this visit, participants will start a 2-week taper and then return to the site 2 weeks later for safety follow-up assessments.

If the participant withdraws consent for disclosure of future information, the sponsor may retain and continue to use any data collected before such a withdrawal of consent.

If a participant withdraws from the study, he/she may request destruction of any samples taken and not tested, and the investigator must document this in the site study records.

7.3 Lost to Follow-up

A participant will be considered lost to follow-up if he/she repeatedly fails to return for scheduled visits without stating an intention to withdraw consent and is unable to be contacted by the study site.

The following actions must be taken if a participant fails to return to the clinic for a required study visit:

- The site must attempt to contact the participant and reschedule the missed visit as soon as possible, counsel the participant on the importance of maintaining the assigned visit schedule and ascertain whether the participant wishes to and/or should continue in the study.
- Before a participant is deemed lost to follow-up, the investigator or designee must make every effort to regain contact with the participant. A minimum of 3 documented attempts must be made to contact any participant lost to follow-up at any time point prior to the last scheduled contact (office visit or telephone contact). At least 1 of these documented attempts must include a written communication sent to the participant's last known address via courier or mail (with an acknowledgment of receipt request) asking that they return to the site for final safety evaluations and return any unused IP. If contact is made but the participant refuses or is unable to return to the site for the early termination and final safety follow-up visit, it should be documented in the eCRF.
- Should the participant continue to be unreachable, he/she will be considered to have withdrawn from the study.

Discontinuation of specific sites or of the study as a whole are handled in [Section 10.1.10](#).

8 STUDY ASSESSMENTS AND PROCEDURES

Study procedures and their timing are summarized in the SOA (see [Section 1.3](#)). Study dates will be based on the date of the first dose of IP and not the date of screening or baseline visits.

Study assessments can be conducted at the institution of the site investigator or remotely at the participant's home. All assessments can be conducted remotely with the use of telemedicine video tools; and for sites located outside of the European Union only, by providing traveling nurses to take vital signs, draw blood samples, and collect specimens.

Immediate safety concerns should be discussed with the sponsor immediately upon occurrence or awareness to determine if the participant should continue or discontinue study intervention.

Adherence to the study design requirements, including those specified in the SOA, is essential and required for study conduct.

All screening evaluations must be completed and reviewed to confirm that potential participants meet all eligibility criteria. The investigator will maintain a screening log to record details of all participants screened and to confirm eligibility or record reasons for screening failure, as applicable.

Procedures conducted as part of the participant's routine clinical management (eg, blood count) and obtained before signing of the informed consent form (ICF) may be utilized for screening or baseline purposes provided the procedures met the protocol-specified criteria and were performed within the timeframe defined in the SOA.

Safety, laboratory, and analyte results that could unblind the study will not be reported to investigative sites or other blinded personnel until the study has been unblinded. Exceptions to this are if there is an urgent medical need ([Section 6.4.2](#)).

8.1 General Study Periods

8.1.1 Screening, Enrollment, Randomization, and Baseline

Potential participants will be pre-identified by the site because of a previous TSC diagnosis based on clinical features and/or [REDACTED] results and those still experience refractory seizures.

The process of identification of participants is performed by the investigator. If an investigator is seeing a patient with TSC in their clinic who is having 8 or more seizures per month, they will make a judgment regarding whether the benefits of clinical trial participation may outweigh the risks of clinical trial participation (with any alternative treatments taken into consideration). If the clinician feels that they do, then they will explain the study to the participant (or LAR). If the participant/LAR is fully informed and provides consent, then this will be documented, and the screening activities can begin.

Note for Investigational Sites in the United Kingdom (UK): National Health Services (NHS) sites in the UK will be aware of the study by virtue of the investigators participating in the site initiation visit, and being trained on the study design, conduct, and participant protection policies.

Informed consent/assent will be obtained after the study has been fully explained to the participant/parent(s)/LAR(s) and before the conduct of any screening procedures or assessments (see [Section 10.1.3](#) for the informed consent procedure). This includes the collection of historical seizure frequency data, or if this information is not available from medical records, the participants will be asked to provide this information for the 8 weeks prior to the Screening Visit based on their own recall/records. This Screening Visit will occur 4 weeks before baseline (Week 0).

At screening, informed consent will be confirmed and the participants eligibility checked. Demographics and Medical history including prior treatment information ([Section 8.1.1.1](#)), historical seizure calendar review ([Section 8.1.1.2](#)), and a seizure identification and diagnostic review ([Section 8.1.1.3](#)) will be performed as well as other study specific procedures as outlined in the SOA ([Table 1](#)).

Randomization will occur approximately 4 weeks after screening at baseline and all participants will be centrally assigned to randomized study intervention (stratified for current CBD use) using an IWRS. Details are provided in [Section 6.4.1](#).

8.1.1.1 Demographics and Medical History

Demographics including age, gender, ethnicity, and race will be collected, as allowed according to local regulations. In addition to the genetic evaluation of pathogenic or likely pathogenic TSC1/TSC2 variant, relevant medical history including but limited to the age of seizure onset, other physical disabilities such as scoliosis, visual impairment, sensory problems, and gastrointestinal difficulties will also be assessed. The participant's developmental history will also be assessed. This will include the grade level of school work that the participant has completed (for individuals who are chronologically school age), as well as the investigator's estimate of the participant's developmental age. Prior medications include all treatment, including but not limited to herbal treatments, vitamins, surgical implants (such as VNS), and prescribed medications received within 30 days (or PK equivalent of 5 half-lives, whichever is longer) of the date prior to screening.

Demographics and Medical History will be reviewed and collected at the Visit 1 (screening). A review of the participant's Medical History will be performed again at Visit 2 (baseline). All findings on the medical history will be recorded on the eCRF. Prior treatment information (therapy name, start and stop date), if available, must be recorded on the appropriate eCRF page.

8.1.1.2 Historical Seizure Calendar Review

A 2-month (8-week) daily historical seizure calendar will be reviewed at the screening visit to determine eligibility per inclusion/exclusion criteria. Acceptable daily historical seizure calendars will need to denote seizure types (or sufficient description), frequency, and days that no seizures occurred.

Procedures specific to this protocol and not otherwise considered standard of care, will not be performed until written informed consent/assent from the participant/parent(s)/caregiver(s)/LAR(s) has been appropriately obtained.

8.1.1.3 Seizure Identification and Diagnostic Review

Per the inclusion criteria, enrollment into the study will be based on the presence and frequency of the primary endpoint seizure types.

Primary endpoint seizure types are defined as the following: focal motor seizures without impairment of consciousness or awareness, focal seizures with impairment of consciousness or awareness with motor features, focal seizures evolving to bilateral, tonic-clonic convulsive seizures, and generalized motor seizures including tonic-clonic, bilateral tonic, bilateral clonic, or atonic/drop seizures. Seizures must have a motor component sufficiently prominent and distinct to clearly establish the observed symptoms as epileptic in origin. Seizures that do not count towards the primary endpoint include: focal or generalized nonmotor seizures (eg, absence seizures or focal nonmotor seizures with or without impairment of awareness), infantile or epileptic spasms, and myoclonic seizures.

To standardize seizure identification and classification in the study, a SIF/DRF will be submitted and reviewed by the Epilepsy Study Consortium. The Epilepsy Study Consortium will review participant seizure data and assign the seizure type for each participant. This categorization of seizure type by the Epilepsy Study Consortium should not delay the participant's entry into the study as this will be determined by the investigator's assessment of eligibility.

Final confirmation and approval of a participant's seizure type is required prior to dispensing the IP.

Instructions for completion of the Seizure Identification and Diagnostic Review Form (SIF/DRF) can be found in the Investigator Site File.

8.1.2 Double-blind Phase

Double-blind treatment with the IP will begin after baseline assessment at Visit 2. All dates during the double-blind phase will be based off the date of randomization and the first dose of the IP. The double-blind phase will include a 4-week titration period (Day 1 to Day 28 inclusive), and a 12-week maintenance period starting on Day 29 to Visit 12 (Week 16).

Participants who discontinue the study prematurely before Visit 12 (Week 16) are required to taper their IP for 2 weeks or shorter, unless otherwise medically indicated. Participants should also complete the eDiary during this time. The end of study assessments, as detailed in the SOA Part A for Visit 13A ([Table 1](#)), should then be performed.

Participants who are not continuing in the OLE will then begin a double-blind taper period where the IP will be withdrawn from Visit 12 (Week 16) as shown in the SOA for Part A as shown in [Table 1](#). This taper period will last for 2 weeks but may be shortened at the discretion of the investigator.

All participants entering the OLE will have their dose of study medication adjusted in a double-blind cross-titration over 4 weeks after Visit 12 (Week 16) as shown in [Table 2](#). This will be performed under blinded conditions and participants previously treated with GNX will complete a dummy titration period.

8.1.3 Safety Follow-up

A safety follow-up visit will be conducted at Visit 13A (Week 20) after a 2- to 4-week down titration for participants who are not continuing in the OLE as shown in the SOA for Part A ([Table 1](#)). This will be the end of study visit for these participants.

For participants who plan to continue in the OLE, additional visits will be conducted as shown in the SOA for Part B ([Table 1](#)).

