[REDACTED] C-SSRS = Columbia-Suicide Severity Rating Scale; ECG = electrocardiogram; eDiary = electronic seizure diary;

ELDQOL = Epilepsy and Learning Disabilities Quality of Life; ET = early termination; HR = heart rate; IP = investigational product; LAR = legally authorized representative; OLE = open-label extension; Peds-QL-FIM = Pediatric Quality of Life - Family Impact Module; PI = principal investigator; PK = pharmacokinetic; QOL = quality of life; RR = respiratory rate; SF-36 = Short Form 36 (version 2); SQS = Sleep Quality Scale; THC = tetrahydrocannabinol; WOCBP = women of childbearing potential.

- Only for participants who discontinue treatment, either early or at Visit 12 prior to down-titration as they are not continuing in the OLE study. This visit will occur 2 weeks after the last dose of IP.
- Written informed consent/assent must be obtained from participant/parent(s)/caregiver(s)/LAR(s) before any study assessments are performed.
- Review of medical history only.

[REDACTED]

- Developmental examination is limited to pediatric participants 1 to 17 years of age, inclusive.

- f. Chemistry and Hematology (See [Section 8.3.4](#))
- g. An attempt should be made to collect a urine sample for a urinalysis at screening. Otherwise, the urine sample can be collected at baseline for the urinalysis.
- h. A plasma (or urine, if plasma is difficult or impossible to obtain) drug screen will be performed to test for THC and non-approved CBD at Visit 1 (screening). A positive test for CBD or THC will exclude the participants from the study, unless the participant is taking prescribed Epidiolex®.
- i. Serum pregnancy test is required for all WOCBP at Visits 1 and 2. At Visits 4, 8, 9, 12, and 13A, the investigator may choose to do either a serum or urine pregnancy test.
- j. PK samples will be collected at these visits; Visit 8 (Week 5): between 1 to 5 hours since last IP dosing, Visit 9 (Week 9): between 4 to 8 hours since the last IP dosing, and Visit 12 (Week 16) where there is no specified time window relative to dosing.

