The participant may have the dose of Investigational Product (IP) temporarily or permanently decreased at any point in the maintenance period to manage tolerability. Additional dosing information can be found in [Section 6.2](#).

Any dose adjustments that are not part of the prespecified titration schedule, including alternative dosing paradigms, should be discussed with the sponsor medical monitor prior to making the change. If it is not possible to contact the medical monitor prior to the dose adjustment, the medical monitor should be notified as soon as possible after making the change.

The maximum dose for all participants is 1800 mg/day. The total double-blind phase (titration and maintenance periods) should not exceed 16 weeks.

Participants who discontinue the IP should undergo a 2-week taper period. The taper period may be shortened at the discretion of the investigator as clinically indicated. Participants who discontinue the IP before the scheduled completion of the study will return to the site 2 weeks after the end of taper to complete the safety follow-up assessments.

Following completion of the double-blind phase, participants who are compliant with study conduct will have the option to enroll and be treated with GNX in a separate open-label extension study (OLE), 1042-TSC-3002. All participants entering the OLE will have their dose of study medication adjusted in a double-blind cross-titration over 4 weeks such that all are receiving GNX at study completion. Participants who do not continue in the OLE will undergo a 2- to 4-weeks double-blind down-titration and taper if discontinuing IP (See [Figure 1](#)).

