6.4.1.1 Study using IWRS

All participants will be centrally assigned to randomized study intervention using an Interactive Web Response System (IWRS). Before the study is initiated, the log-in information and directions for the IWRS will be provided to each site. An IWRS will be utilized for the following IP tasks:

- Randomization, stratified for current CBD use.
- Supply management.
- Inventory management and supply ordering.
- Expiration date tracking.
- Emergency unblinding.

An IWRS will centrally randomize participants. The randomization schedule (comprised of a kit list and randomization list) will be generated using standard, validated methods, and maintained by the respective supplier and IWRS vendor. The investigator will be instructed by the IWRS, which numbered bottle to use to dose a participant. The investigator and research staff will be aware of the ascending dose design of the clinical investigation; however, the investigator, the research staff, and the participants will be blinded with respect to who is receiving active drug versus placebo. The maximum placebo period is 18 weeks.

The contents of each bottle will be blinded using labels. The randomization schedule will match a participant number to a bottle number. Upon completion of baseline evaluations for each participant, the investigator or appropriate designee will log into the IWRS to receive a bottle number allocated according to the randomization schedule. Complete instructions for obtaining a bottle number will be provided to the clinical sites prior to initiating the study. The designated personnel at the clinical site will match the assigned bottle number with the correct bottle of IP and distribute the bottle to the investigator or designee.

Study medication will be dispensed at the study visits as summarized in the SOA ([Section 1.3](#)).

Returned study medication should not be redispensed to the participants.

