1. INTRODUCTION

This is a Phase 3, global, double-blind, randomized, placebo-controlled study of adjunctive Ganaxolone (GNX) treatment in children and adults with TSC-related epilepsy. The study consists of a 4-week prospective baseline phase, defined as the first 28 days following screening, followed by a double-blind phase consisting of a 4-week titration period and a 12-week maintenance period.

Following completion of the treatment period, participants who are compliant with study conduct will have the option to enroll and be treated with GNX in a separate OLE study, 1042-TSC-3002. All participants entering the OLE will have their dose of study medication adjusted in a double-blind cross-titration over 4 weeks such that all are receiving GNX at study completion. Participants who do not continue in the OLE will undergo a 2- to 4-week double-blind down-titration and taper if discontinuing IP.

Sections 2 and 5 of the Protocol provides a detailed description of the investigational product, target patient population, and potential risks and benefits of treatment with GNX. The purpose of this Statistical Analysis Plan (SAP) is to define the methodology for analyzing and summarizing the data collected during the conduct of Study 1042-TSC-3001.

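### For participants not entering the extension, the stated taper lengths, the Week 20 safety visit, its 2-weeks-after-last-dose timing and the 18-week placebo maximum cannot all hold once the taper exceeds 2 weeks

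*Protocol*

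**What the plan says.** All of the following concerns participants who reach Week 16 and do not enter the extension study.

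- **Taper length, 2 to 4 weeks.** Protocol 4.1: "Participants who do not continue in the OLE will undergo a 2- to 4-weeks double-blind down-titration and taper if discontinuing IP". The synopsis (1.1), schema footnote d (1.2) and section 4.1.1 say the same, and section 8.1.3 places the safety visit "after a 2- to 4-week down titration for participants who are not continuing in the OLE". SAP section 1 repeats the range: "Participants who do not continue in the OLE will undergo a 2- to 4-week double-blind down-titration and taper if discontinuing IP".
- **Taper length, 2 weeks at most.** Protocol 8.1.2, for non-extension participants from Visit 12 (Week 16): "This taper period will last for 2 weeks but may be shortened at the discretion of the investigator".
- **Visit 13A by calendar.** Table 1 and section 8.1.3 fix it at Week 20. Table 1 gives a window of ±7 days, and schema footnote d puts the visit at the end of 4 weeks.
- **Visit 13A by last dose.** Table 1 footnote a: "This visit will occur 2 weeks after the last dose of IP". The footnote expressly includes participants who stop at Visit 12 because they are not continuing, so it is not a rule for early terminators alone. The synopsis also times the follow-up at 2 weeks from the final dose.
- **After stopping treatment.** Section 7.1: "These participants will have a visit 2 weeks after the end of taper to complete the safety follow-up assessments". Section 7.2: "participants will start a 2-week taper and then return to the site 2 weeks later for safety follow-up assessments".
- **Placebo maximum.** Section 6.4.1.1: "The maximum placebo period is 18 weeks".

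**The concern.** Visit 13A is timed in two ways, by study week and by last dose. The two agree only if the taper has one particular length, yet the taper length is itself stated in two ways. A site that uses the upper end of the range in sections 4.1 and 8.1.3 departs from section 8.1.2, and it cannot meet both Visit 13A timings.

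What is at stake is safety observation after withdrawal of a centrally acting drug. Section 8.1.3 makes Visit 13A the end-of-study visit, and Table 1 schedules adverse events, C-SSRS, vital signs and pregnancy testing there. Section 8.3.5 asks for close monitoring of suicidality around the end of treatment and dose changes. No scheduled assessment follows, and section 8.4.1 does not oblige investigators to look for events actively after participation ends. If the off-drug interval at Visit 13A depends on which sentence is followed, the withdrawal-period data are not comparable across participants. The stated placebo maximum would also be wrong for some of them.

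**Working it through.** **Inputs.** Taper starts at Week 16 (8.1.2). Visit 13A is at Week 20 ±7 days, that is Weeks 19 to 21 (Table 1). The alternative anchor is last dose + 2 weeks (footnote a). The Visit 12 window is ±3 days (Table 1).

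**Formulas.**
- Last dose (week) = 16 + taper.
- Off-drug days at Week 20 = 7 × (20 − last dose).
- Visit week under footnote a = last dose + 2.
- Weeks of blinded treatment, which for the placebo arm is the placebo period = 16 + taper.

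**The plan's own figures first.** With a 2-week taper, 16 + 2 = 18, the stated placebo maximum, and 18 + 2 = 20, the stated visit week. Both reproduce.

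**Other taper lengths.**

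| Taper (weeks) | Last dose (week) | Off-drug days at Week 20 | With ±7-day window | Visit week under footnote a | Weeks of blinded treatment |
|---|---|---|---|---|---|
| 1 | 17 | 21 | 14 to 28 | 19 | 17 |
| 2 | 18 | 14 | 7 to 21 | 20 | 18 |
| 3 | 19 | 7 | 0 to 14 | 21 | 19 |
| 4 | 20 | 0 | −7 to +7 | 22 | 20 |

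**Reading the table.**
- Nominally, Week 20 and footnote a coincide only at a 2-week taper.
- At 3 weeks, both can be met only at the late edge of the window (Week 21), and blinded treatment is already 19 weeks against the stated 18.
- At 4 weeks, both cannot be met. A visit 2 weeks after the last dose is at Week 22, one week beyond the window.
- Adding the ±3-day Visit 12 window widens the 4-week range to −10 to +10 days, still short of 14.
- A 1-week taper also departs from the nominal Week 20, but it can meet both timings at the early edge of the window (Week 19) and does not exceed the placebo maximum.

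**The case against.** The strongest reply is that much of the operative text fits a single scheme. Sections 6.2 and 7.1, the synopsis paragraph on intervention duration, section 8.1.2, footnote a and the 18-week figure all fit a 2-week taper followed by 2 weeks of observation. No dosing table sets out a 4-week taper. On this view the 2- to 4-week phrase is loose shorthand for the interval from Week 16 to Week 20. That may explain how the wording arose, but section 8.1.3 places the visit after the 2- to 4-week down-titration, so the text does not say it. The SAP carries the same phrase.

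Three further objections stand in part.

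- A reader might infer that a 4-week taper leaves no off-drug safety observation. The documents do not support that. Zero days is the nominal result only if Week 20 overrides footnote a. The window alone allows up to 7 days, and following footnote a keeps 14 days but moves the visit to Week 22. Section 8.4.1 also requires adverse events to be followed to closure and keeps later-discovered related serious events reportable. These provisions do not replace a scheduled C-SSRS or vital-sign assessment.
- A reader might infer that section 7.2 contradicts section 7.1. Its wording leaves open whether the 2 weeks run from the start or the end of the taper, and the sequential reading agrees with 7.1. It is ambiguous, not contradictory.
- Section 8.1.2 is not an absolute cap for everyone. Its sentence on premature discontinuers allows medical exceptions. The conflict rests on its separate sentence about participants who reach Week 16 and do not continue.

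**Conclusion.** The inconsistency is real and is in current text. It concerns the same participants and the same visit. For a 4-week taper, which several sections permit, Visit 13A either has nominally 0 days off drug (−7 to +7 with its window) or falls at Week 22, outside the window. Blinded treatment is 20 weeks, 2 more than the stated maximum. For a 3-week taper, a Week 20 visit has nominally 7 days off drug.

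This rests on the taper starting at Week 16, as section 8.1.2 states, and on the 18-week figure meaning 16 weeks plus taper. The protocol does not show how that figure was derived. The documents give no number for participants who will decline the extension or be tapered for more than 2 weeks, so the number affected cannot be sized. The consequence is confined to withdrawal-period safety data and consistency of conduct; nothing here bears on the power or validity of the efficacy comparison. No view is taken on which taper length or visit timing is right.

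**What to change.** Reconcile Protocol sections 1.1, 1.2, 1.3 (Table 1 footnote a and the Visit 13A week), 4.1, 4.1.1, 6.2, 6.4.1.1, 7.1, 7.2, 8.1.2 and 8.1.3, and SAP section 1. One statement of taper length, one of Visit 13A timing relative to the last dose, and one of the maximum placebo period should apply throughout. In section 7.2, say whether the 2 weeks before the return visit run from the start or the end of the taper. The sponsor's clinical team decides which statement governs. After that choice, repeat the calendar check above so that the visit week, its window and the placebo maximum all follow from it.

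The cost is wording: a clarification letter or the next protocol amendment, with a matching edit to the SAP introduction. The sample size and the efficacy analyses do not change.
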